9.5.1 Analyses of Primary Efficacy Endpoint(s)

For the primary analyses, the continuous primary endpoints will be tested using a generalized linear mixed model based on observed monthly data from 12-week DBTP with appropriate contrasts provided in [Appendix B](#) for pairwise treatment comparisons and overall linear trend.

The model will include treatment group, baseline value, stratification factors which include region (North America vs Rest of World) and **baseline migraine frequency type (CM vs. EM)**, scheduled visit, the interaction of treatment group with scheduled visit using the PAS without any imputation for missing data. If applicable, the first-order autoregressive covariance structure is assumed. Least squares means (LSMs) for each treatment group, standard errors, associated 95% confidence intervals, difference of LSMs compared to placebo group, associated 95% confidence intervals and unadjusted two-sided p-values will be tabulated by visit and treatment, as well as for the mean monthly values over the last month in the DBTP.

The primary endpoint, change in monthly migraine days from baseline to the last 4 weeks of the 12-week double-blind treatment phase, will be tested for each AMG 301 treatment group (the AMG 301 420 mg SC injections Q2W and AMG 301 210 mg SC injections Q4W) compared to the placebo group using appropriate contrasts for pairwise comparisons. Each AMG 301 dose will be compared to placebo at an alpha of 0.05 to maintain the family-wise type I error at 0.10. The mean change from the baseline period for each treatment group, and the treatment difference, 95% confidence intervals, and p-values will be reported.

Sensitivity analyses for the primary endpoint include subgroup analyses and an analysis of covariance model using data through week 12 data, in which missing values for continuous variables will be imputed by multiple imputation with the assumption of MNAR up to week 12. For dichotomous endpoints, missing values will be imputed by the NRI method. Sensitivity analysis described below will be performed for the primary endpoint:

Summary statistics and ANCOVA model for continuous endpoint. Factors of treatment, baseline covariate and stratification variables will be included in the model. MI with assumption of MNAR (control-based pattern imputation) for continuous endpoints.

- 1. Primary endpoint will be summarized by the subgroup of**
 - Region (North America, Rest of World)**
 - Migraine type (EM, CM)**

- **Prior use of anti-CGRP medication (yes, no)**
- **Prior migraine prophylactic treatment failures (1, \geq 2)**
- **Medication overuse (yes, no)**
- **CAPS score (0, \geq 1)**
- **Age (< median, \geq median)**
- **Sex (female, male)**
- **Race (White, Other)**
- **Response status to AMG 334 (yes, no)**

The purpose of the subgroup analyses is to explore if the treatment effect varies across subgroups of interest. Subgroup analyses are performed for primary efficacy endpoint using the same method as primary analysis method but performed within each interested subgroup. The treatment difference (or odds ratio) with associated 95% confidence intervals and p-values will be reported within each subgroup.

Note: if the subgroup is one of the stratification factors, the stratification factor will not be included in the model, but the other randomized stratum will be included (ie, if the subgroup is prophylactic migraine medication, then randomized region would be included in the model instead of randomized strata which combined both stratification factors). **These subgroups will be re-examined for appropriateness and may be re-categorized (due to small sample size, for example, if there are < 10% of subjects within a subgroup) before unblinding. The analyses of these subgroups will be exploratory in nature.**

The heterogeneity of the treatment effect across the subgroups will be evaluated for the primary endpoints by examining the treatment by subgroup interaction and a p-value will be presented. For continuous endpoints, the primary analysis model with the addition of treatment group by subgroup interaction will be used.

Primary summary and analysis method with treatment and stratification interaction for continuous endpoints: the interaction of treatment group by stratification variable will be tested with significant level of 0.15. If the interaction term is significant, the interaction term will be included in the model as sensitivity analysis for the primary analysis method.

Time from last dose of study drug to loss of response will be evaluated during the Safety Follow-up period. For responders, loss of response is defined as the first time the subject returns to < 50% reduction from the baseline period in monthly migraine days. For non-responders, loss of response will be evaluated by

percentage of reduction from the baseline period in monthly migraine days over time.

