5.4 Study Time Intervals

Monthly Interval for Efficacy Endpoints

Monthly efficacy measurements will be calculated based on the 2-week IP dosing schedule defined below using eDiary data collected from the beginning of the baseline phase (week -4 visit) up to the end of the safety follow-up phase (week 28 end of eDiary use). Any eDiary data occurring after EOS date or after the end date of the last monthly interval defined below, whichever comes earlier, will not be included in the analysis.

Table 5-1. Monthly Interval for Efficacy Endpoints Derived From Daily eDiary Data

Study Phase	Assessment Time Point	Monthly Interval	
		Start Date/Day	End Date/Day
Baseline Phase	Baseline	eDiary device assignment date (week -4 visit)	The day of or prior to Study Day 1
Double-blind Treatment Phase	Week 4	Study Day 1	
• Week 4 dose date – 1• Else MIN(Study Day 28, EOS) if Week 4 dose was not received
	Week 8	
• Week 4 dose date• Else Study Day 29 if Week 4 dose was not received	
• Week 8 dose date – 1• Else MIN(Study Day 56, EOS) if Week 8 dose was not received
	Week 12	
• Week 8 dose date• Else Study Day 57 if Week 8 dose was not received	
• MIN(Study Day 84, EOS)
Safety Follow-up Period	Week 16	
• Study Day 85	
• MIN(Study Day 112, EOS)
	Week 20	
• Study Day 113	
• MIN(Study Day 140, EOS)
	Week 24	
• Study Day 141	
• MIN(Study Day 168, EOS)
	Week 28	
• Study Day 169	
• MIN(Study Day 196, EOS)

Study Visit

Since the actual visit for a subject may not exactly coincide with their targeted visit date, the actual visit date is mapped to the study visit as following. The study day window will be utilized to define study visit for lab, vital signs, physical measurements and PROs collected during office visits including HIT-6, and MMIDAS. Any data occurring after the EOS date will not be included in the analysis with the exception of lab shift analyses and antibody data.

Table 5-2. Study Visit Windows for HIT-6, MMIDAS, C-SSRS, and CAPS Scale

Study Phase	Study Visit	Target Day	Study Day

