8.3.3 Missing Post-baseline Evaluation in the DBTP

Primary analysis of continuous efficacy endpoints during the 12-week randomized DBTP will be conducted using the generalized linear mixed model on observed data without subject-level imputation.

In sensitivity analyses of primary and secondary efficacy endpoints during the 12-week DBTP, missing continuous monthly efficacy endpoints will be handled using multiple imputation (MI) with the assumption of missing not at random (MNAR) (with control-based pattern imputation). The continuous monthly efficacy endpoints will be computed as the mean over the last four weeks of the DBTP based on the observed and imputed values.

In the non-responder imputation (NRI) method, post-baseline missing dichotomous efficacy endpoints (**responder [Yes/No] based on $\geq 50\%$, $\geq 75\%$ and 100% reduction from baseline in monthly migraine days**) during the DBTP will be imputed as

non-responder at each corresponding time point. The dichotomous endpoints derived based on the mean change from baseline over the last 4 weeks of the DBTP will be imputed as non-responder if the mean change from baseline over the last 4 weeks of the DBTP is missing.

If the proportion of missing data for the primary endpoint is high (eg, > 20%), further analyses will be performed to

- examine the frequency and reason of missing data
- determine if there are any patterns in the missing data
- distinguish true missing values from other unknown values (eg, due to measurement or sample processing error)

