For primary analysis at week 12, the continuous change from baseline efficacy endpoints calculated by the method as specified in [Section 5.6](#) will be analyzed using generalized linear mixed effect models including treatment group, stratification factors, scheduled visit, the interaction between treatment group and scheduled visit and the baseline value on observed data. The dichotomous efficacy endpoints will be analyzed using the stratified Cochran-Mantel-Haenszel (CMH) test after the missing data are imputed as non-response. Detailed primary analysis methods, sensitivity analyses, and covariates included in the models are summarized in the table below.

Table 9-1. Summary of Efficacy Endpoints and Analysis Methods

Endpoint	Primary Summary and Analysis Method	Sensitivity Analysis
Primary Endpoint		
Change in monthly migraine days from baseline to the last 4 weeks of the 12-week DBTP (Note: Results from time points other than week 12 during the DBTP will also be generated in the same generalized linear mixed effect model.)	Analysis Method I: 1. Summary statistics by visit using observed data 2. Least squares means from a generalized linear mixed effect model including treatment group, baseline values, stratification variables, scheduled visit, and interaction of treatment and scheduled visit using observed data	1. Summary statistics by visit and analyze using an ANCOVA model with multiple imputation assuming MNAR(control-based pattern imputation) 2. Summary statistics by visit and analyze using an ANCOVA model with observed data 3. Subgroup analyses: Same as primary summary and analysis method.

Page 1 of 3

Footnotes defined on last page of the table

Table 9-1. Summary of Efficacy Endpoints and Analysis Methods

Endpoint	Primary Summary and Analysis Method	Sensitivity Analysis
Secondary Endpoints		

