At least a 50% reduction from baseline in monthly migraine days in the last 4 weeks of the 12-week DBTP (Note: Results from time points during DBTP will also be generated in the same model.)	1. Summary statistics by visit using observed data 2. Stratified Cochran-Mantel-Haenszel (CMH) Test	1. Summary statistics by visit and analyze using a logistic regression model, and using responder rate calculated using monthly migraine days 2. A stratified Cochran-Mantel-Haenszel (CMH) test will be used after the missing data are imputed as non-response 3. A generalized linear mixed effects model will be used on observed data 4. Subgroup analyses: Same as primary summary and analysis method.
Change from baseline in monthly acute migraine-specific medication treatment days in the last 4 weeks of the DBTP (Note: Results from individual time point during the DBTP will also be generated in the same generalized linear mixed effect model.)	Analysis Method I (see above)	Analysis Method II: 1. Summary statistics by visit and analyze using an ANCOVA model with multiple imputation, assuming MNAR
Change from baseline in monthly physical impairment scores as measured by MPFID at assessment time points (Note: Results from individual time point during the DBTP will also be generated in the same generalized linear mixed effect model.)	Analysis Method I	N/A

Footnotes defined on last page of the table

Page 2 of 3

Table 9-1. Summary of Efficacy Endpoints and Analysis Methods

Endpoint	Primary Summary and Analysis Method	Sensitivity Analysis
Change from baseline in monthly impact on everyday activities scores as measured by MPFID at assessment time points (Note: Results from individual time point during the DBTP will also be generated in the same generalized linear mixed effect model.)	Analysis Method I	N/A
CCI	Analysis Method I	N/A
	
• Summary statistics by visit using observed data• Stratified CMH test	N/A

Page 3 of 3

^a The same analyses methods will be applied to the endpoints:

Change from baseline in headache impact scores as measured by HIT-6
Change from baseline in monthly average severity of migraine pain
Change from baseline in monthly acute headache medication treatment days.
Change from baseline in migraine-related disability and productivity as measured by MMIDAS
Change from baseline in monthly days with physical impairment as measured by the MPFID

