9.5.2 Analyses of Secondary Efficacy Endpoint(s)

For continuous secondary efficacy endpoints, summary statistics and primary analysis method will be conducted in the same way as that for the primary endpoints as specified in [Section 9.5.1](#).

For dichotomous secondary endpoints, comparison between treatment arms will be performed using a stratified CMH test for the primary analysis. Sensitivity analyses will use generalized linear mixed effects model on observed data, adjusting for baseline values and stratification factors with appropriate contrasts for pairwise comparisons. The odds ratio for each AMG 301 treatment group versus placebo group, associated 95% confidence intervals, and unadjusted p-values will be reported. Sensitivity analyses for response include: a logistic regression model using data through week 12, adjusting for baseline values where missing values will be imputed as non-responders.

Subgroup analyses are performed for secondary efficacy endpoints using the same method as primary analysis method but performed within each interested subgroup. The treatment difference (or odds ratio) with associated 95% confidence interval and p-values will be reported within each subgroup.

CCI

A large black rectangular box redacting content. The text 'CCI' is visible in the top-left corner of the redacted area.

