9.5.4 Analyses of Clinical Outcome Assessments (COAs) and Patient Reported Outcomes (PROs)

The COAs and PROs include MPFID, HIT-6, MMIDAS and CAPS. Change from baseline in total score (or subscale if applicable) of each COA and PRO (except endpoints described in the [Section 9.5.1](#) above) will be reported during the DBTP.

For HIT-6, in addition to the analysis of continuous change from baseline value, proportions of subject with a \geq 5-point reduction from baseline and proportions of subject with HIT-6 \geq 60 (severe impact) will be analyzed similarly as the primary analysis method for dichotomous efficacy endpoints described in [Section 9.5.2](#) above. No sensitivity analysis will be conducted for COA and PROs except for MPFID. The PAS will be used to analyze COA and PRO endpoints.

Table 9-2. Summary of COA and PRO Endpoints and Analysis Methods

Endpoint	Primary Summary and Analysis Method
Change from baseline in the daily activity impact of a headache as measured by the HIT-6 total score	1. Summary statistics by visit using observed data 2. Least squares mean at each time point calculated based on a linear mixed effects model including treatment group, baseline value, stratification factors, scheduled visit, and the interaction of treatment group with scheduled visit, without any subject-level imputation for missing data.
Change from baseline in CAPS	Same as above
Change from baseline in migraine-related disability and productivity as measured by the modified MIDAS (Note: MIDAS scores are collected every month. The first post-baseline measurement of the modified MIDAS scores are at week 4)	Same as above; using ANCOVA model instead of generalized linear mixed effect model.
Change from baseline in monthly mean overall impact on everyday activities score as measured by MPFID stand-alone item	Same as above; using ANCOVA model instead of generalized linear mixed effects model.
Change from baseline in monthly days with physical impairment as measured by MPFID	Same as above; using ANCOVA model instead of generalized linear mixed effects model.
HIT-6 severity grade shift from baseline	Summary statistics for DBTP only. Shift table will also be provided to compare baseline values vs the most extreme post-baseline values through the DBTP.
MMIDAS severity grade shift from baseline	Summary statistics for DBTP only. Shift table will also be provided to compare baseline values vs the most extreme post-baseline values through the DBTP.

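### The primary model's only readable covariance statement is a conditional AR(1); if it means one common variance, the Week 12 standard error is borrowed from Weeks 4 and 8

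*SAP*

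**What the plan says.** SAP 9.5.1 fits one mixed model to the observed monthly values of the double-blind period. Its terms are treatment, baseline, the two stratification factors, visit and treatment by visit, and missing values are not imputed. SAP 5.4 ("Table 5-1. Monthly Interval for Efficacy Endpoints Derived From Daily eDiary Data") divides that period into three intervals, Weeks 4, 8 and 12. The primary test is the Week 12 contrast of each dose with placebo, and the error claim is: "Each AMG 301 dose will be compared to placebo at an alpha of 0.05 to maintain the family-wise type I error at 0.10".

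On the within-subject covariance, 9.5.1 says "If applicable, the first-order autoregressive covariance structure is assumed". SAP 9.1 and 9.5 list only fixed effects, and protocol 10.4.3.2 names only the model class. The code in Appendix B is redacted.

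The same model is carried further in SAP 9.5.2: "For continuous secondary efficacy endpoints, summary statistics and primary analysis method will be conducted in the same way as that for the primary endpoints".

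**The concern.** A homogeneous AR(1) structure has two parameters: one variance shared by all visits and one correlation. The trial's main conclusion concerns Week 12 alone. If migraine-day counts are more variable at Week 12 than on average over the three months, the shared variance understates the Week 12 standard error. Both primary p-values are then too small and the confidence intervals too narrow. If Week 12 is less variable than average, the trial loses power. With dropout, the imposed pattern corr(W4,W12) = corr(W4,W8)² also enters the estimate.

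The opening condition adds a second problem. With no readable definition and no named alternative, the structure behind the primary p-value can still be chosen after the data are seen.

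**Working it through.** **Inputs from the documents.** Three visits (SAP Table 5-1); about 335 subjects allocated 4:3:3 (SAP 3.1); two-sided tests at 0.05 each, family-wise 0.10 (SAP 2.2, 9.5.1). Effect size, SDs, power and expected dropout are redacted. Every SD, correlation and dropout rate below is therefore an assumption.

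**Step 1: the plan's own figure.** 0.05 + 0.05 = 0.10, so the bound reproduces. The two tests share a placebo arm; under 4:3:3 their correlation is √(3/7 × 3/7) = 3/7. The bivariate normal then gives an actual family-wise error rate (FWER) of 0.093, a margin of about 0.007.

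**Step 2: what the shared variance becomes.** Minimising log|S| + tr(S⁻¹V) over the two AR(1) parameters gives the large-sample fit. The check uses a true correlation of 0.65 between all visits.

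- SDs 4.5, 4.95, 5.4: √[(20.25 + 24.50 + 29.16)/3] = 4.96; fitted SD 4.97.
- SDs 5.4, 4.86, 4.32: √[(29.16 + 23.62 + 18.66)/3] = 4.88; fitted SD 4.88.

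So model-based SE / true SE at Week 12 is very nearly r = √(mean of the three variances) / SD at Week 12.

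**Step 3: consequence.** Per-test error = 2[1 − Φ(1.96 r)]. FWER comes from the bivariate normal with correlation 3/7 and critical value 1.96 r. Power for a comparison with 80% under a correct SE = Φ(1.96 + 0.84 − 1.96 r). Brackets give the range when Week 8 equals Week 4 or Week 12 instead of lying midway.

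| Week 12 / Week 4 SD | r, Week 8 midway | FWER | Power |
|---|---|---|---|
| 0.8 | 1.130 | 0.051 (0.041–0.061) | 72% (69–75%) |
| 0.9 | 1.057 | 0.072 (0.066–0.078) | 77% (76–78%) |
| 1.0 | 1.000 | 0.093 | 80% |
| 1.1 | 0.955 | 0.112 (0.105–0.120) | – |
| 1.2 | 0.919 | 0.131 (0.116–0.146) | – |

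FWER reaches 0.10 at r = 0.9824, that is, with the Week 12 SD 1.8% above the pooled SD. As a Week 12/Week 4 ratio this is 1.037 with Week 8 midway, 1.027 if Week 8 equals Week 4, and 1.057 if it equals Week 12. Just beyond that the excess is trivial (0.1007 at 1.04, midway).

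**Step 4: other readings of the sentence.** Using the two SD sets of Step 2:

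- A random intercept, alone or with AR(1), changes nothing: FWER 0.131 and 0.051.
- A random intercept plus slope largely removes the problem: 0.096 and 0.086.
- A heterogeneous AR(1) removes it: 0.093.

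**Step 5: simulation with dropout.** REML fits, 134/101/100 subjects, 4,000 trials, Monte Carlo SE about 0.005, dropout depending on the previous value. FWER:

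| SD ratio, dropout | AR(1) | Het. AR(1) | Het. Toeplitz | Unstructured | Observed ANCOVA |
|---|---|---|---|---|---|
| 1.2, 10% | 0.127 | 0.090 | 0.094 | 0.094 | 0.096 |
| 1.2, 20% | 0.127 | 0.085 | 0.090 | 0.090 | 0.092 |
| 1.0, 20% | 0.086 | 0.088 | 0.091 | 0.091 | 0.093 |
| 0.8, 10% | 0.052 | 0.088 | 0.093 | 0.092 | 0.096 |

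The 20% level is the threshold in SAP 8.3.3: "If the proportion of missing data for the primary endpoint is high (eg, > 20%), further analyses will be performed to". At ratio 0.8 with 10% dropout, power was 68% under AR(1) against 77% unstructured. With equal SDs and 20% dropout, the correlation pattern alone cost about 1 point of power (74.5% against 75.8%).

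A separate, simpler simulation used 800 trials, no baseline or strata, and 10% missing at Week 12. With SDs 3.2/3.6/4.0 the chance of any rejection was 15.3% under AR(1) and 9.9% unstructured. With 4.8/4.4/4.0 it was 4.1% and 7.9%.

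**The case against.** The strongest reply is that Appendix B is code and is redacted. It may fix a heterogeneous form, a robust standard error or a fallback, and redacted text cannot be counted as absent. That stands. It limits the point to the readable text and makes every consequence conditional. It does not repair the sentence in 9.5.1, which remains conditional and undefined.

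Second, harm needs several things at once: the homogeneous form, model-based standard errors, no random slope, and unequal visit variances. None is established. That also stands, and is why this is a vulnerability and not an error.

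Third, Table 9-1 already plans, for the primary endpoint, "Summary statistics by visit and analyze using an ANCOVA model with observed data". Run at Week 12, it uses the Week 12 variance and would expose a material discrepancy. But it is a sensitivity analysis: it neither sets the primary p-value nor is named as a replacement. For the two MPFID domain scores Table 9-1 lists no sensitivity analysis at all. SAP 9.5.4 says "No sensitivity analysis will be conducted for COA and PROs except for MPFID" but names no method for MPFID.

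Fourth, a parsimonious structure is a legitimate choice in a phase 2a trial, and the opening condition may only separate repeated-measures endpoints from those analysed by ANCOVA. Both are possible. Even so, the saving is from 6 parameters to 2 with about 335 subjects, which the data do not require.

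The simulation has limits. About 11% of fits over all structures, including a random-slope model whose simulated results are not used, stopped at the iteration cap. This is not broken down by structure. Kenward-Roger itself was not simulated. The large-sample calculation and the second simulation agree with it in direction, and the conclusion does not depend on its third decimal.

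**Conclusion.** The point holds as a recommended change. In the readable plan, the p-values and intervals of both primary comparisons may rest on an equal-variance assumption that is neither justified nor needed. Assuming a homogeneous AR(1) with model-based standard errors, Week 12/Week 4 SD ratios from 0.8 to 1.2 move the family-wise error between about 0.04 and 0.15. Rising SDs inflate it, falling SDs cost up to about 11 points of power (80% to 69%), and equal SDs do no harm. Which case applies cannot be known from the documents. If the code already allows visit-specific variances, only the wording needs correcting.

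**What to change.** Replace the covariance sentence in SAP 9.5.1 with:

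> An unstructured covariance matrix will be used for the within-subject errors. If the model does not converge, a heterogeneous Toeplitz structure and then a heterogeneous first-order autoregressive structure will be used, in that order. Degrees of freedom will be computed by the Kenward-Roger method.

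Apply it to the primary endpoint and to the continuous secondary endpoints under Analysis Method I: acute migraine-specific medication days and the two MPFID domain scores. If the Appendix B code already allows visit-specific variances, state that structure in the text instead.

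The cost is one sentence and the matching line of code, four more covariance parameters (6 against 2), and a small risk of non-convergence. With three visits heterogeneous Toeplitz saves only one parameter over unstructured (5 against 6), so heterogeneous AR(1), with 4, is the more useful fallback; both keep a separate Week 12 variance.

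One related matter needs separate reconciliation. MMIDAS, MPFID physical-impairment days and the MPFID overall-impact score fall under the mixed model through footnote a of Table 9-1 but under ANCOVA in Table 9-2. This sentence does not settle them.
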